11.2 Sample Size/Accrual Rate

We plan on recruiting 300 subjects over the course of a year, with the anticipation that 120 will participate in the study to completion. This means we hope to recruit approximately 25 subjects per month.

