WCM	Weill Cornell Medicine

Protocol Summary

Please provide a brief protocol summary.

Full Title:	Mobile Cognitive Behavior Therapy Targeting Anxiety Disorders
Short Title:	Mobile CBT in Anxiety
Clinical Phase:	N/A – no drug or device involved
Principal Investigator:	[name]
Sample Size:	N = 120
Accrual Ceiling:	We plan to screen up to 300 subjects.
Study Population:	18-25 year olds who have been diagnosed with an anxiety disorder as per the Anxiety Disorders Interview Schedule.
Accrual Period:	We anticipate complete accrual of participants taking up to 1 year
Study Design:	Participants in this study will use an online Cognitive Behavior Therapy program to assist with treatment of their anxiety symptoms. This program is being developed by Weill Cornell Medicine faculty as part of the University of Pennsylvania Center for Health Incentives and Behavioral Economics's established online platform called "Way to Health." All participants in the study will be using the program; as this is a pilot study testing the feasibility of using an online CBT program plus non-monetary incentives. Participants will be told to use the program for at least 20 minutes per day, 2 days per week, for up to 6 weeks. Participants will check in once a week in person or over the phone or a HIPAA-compliant virtual meeting platform. There will also be one follow up visit 6 weeks after they have stopped using the program.
Study Duration:	3 months
Study Agent/	
Intervention Description:	There is no drug or invasive device being used; rather, we are simply providing an online Cognitive Behavior Therapy program through an existing online platform called "Way to Health"
Primary Objective:	The primary objective is to examine different ways of motivating people to make use of the online therapy program, and to assess whether social supports are as efficacious, or more efficacious, than a reward mechanism such as non-monetary incentives. We will randomize subjects to one of three conditions: a social support condition, a gain-framed condition in which participants can earn "points" for completing their assigned sessions, and a

loss-framed condition in which participants lose “points” for failing to complete their assigned sessions on time. We will compare change in anxiety from baseline to end of treatment between these three conditions.

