5.1 Schedule of Evaluations

5.1.1 Screening Visit

This assessment will take place either in person, over the phone, or on a HIPAA-compliant virtual meeting platform. Decisions about how visits will take place will be made with participants, depending on safety and convenience.

- Anxiety Disorders Interview Schedule (ADIS) to get a Clinical Severity Rating (CSR) must be 4 or higher to receive a primary diagnosis of Anxiety Disorder, and no other psychiatric conditions can have a higher CSR).
- We will collect contact information so that we can follow up with the participant after the evaluation.
- We will also collect medication and psychiatric treatment information to determine study eligibility.

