5.1.2.1 Visit 1: Baseline

- Participants are randomized to one of three incentive conditions (gain-framed points, loss-framed points, or social support). Participants in the social support condition will identify a person in their life who will receive

text message updates about their progress—or they can choose to have the study team receive the updates.

- Demographic Information
- Test of Premorbid Functioning for Wechsler Intelligence Scale for Adults (WAIS) unless completed within 18 months.
- Rumination Response Scale (RRS)
- Hamilton Rating Scale for Depression (HAM-D)
- Hamilton Rating Scale for Anxiety (HAM-A)
- Anxiety Sensitivity Index (ASI-3)
- Liebowitz Social Anxiety Scale (LSAS)
- Generalized Anxiety Disorder 7-item Scale (GAD-7)
- Patient Health Questionnaire 9 (PHQ-9)
- The Temporal Experience of Pleasure Scale (TEPS)
- Positive and Negative Affect Schedule (PANAS)
- Emotion Regulation Questionnaire (ERQ)
- Multidimensional Experiential Avoidance Questionnaire (MEAQ)
- Pittsburgh Sleep Quality Index (PSQI)
- World Health Organization Quality of Life short-form scale (WHOQOL-BREF)
- Life Events Scale for Students (LESS)
- Sensitivity to Punishment and Sensitivity to Reward Questionnaire (SPSRQ)
- Multidimensional Assessment of Interoceptive Awareness (MAIA)
- Digital Working Alliance Inventory (D-WAI)
- Medication Tracking
- Optional MRI Tasks: Points Incentive Delay Task, Social Incentive Delay Task
- Optional EEG

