5.2 Treatment Administration

Treatment will be administered on an *outpatient* basis.

Participants will be asked to engage with the mobile application at least 2 days a week

Protocol # 1803019086

Version Date 12/27/2022

for 20-25 minutes per session. These sessions can be done at the participants' convenience for various lengths of time. These tasks can be boring or frustrating for

some people, but participants are allowed to take breaks, or to make sessions shorter. Participants may also decide to stop participating at any time.

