5.4 Duration of Therapy and Criteria for Removal from Study

In the absence of treatment delays due to adverse event(s), treatment may continue for 12 weeks or until one of the following criteria applies:

The study will take place for a total of 6 weeks but participants will continue to have access to the mobile device if they would like to after the study is complete. Participants are welcome to withdraw from the study at their own discretion. There are no general or specific changes in the patient's condition that would render the patient unacceptable for further treatment in the judgement of the investigator.

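### Does 120 as both the sample size and the number of completers mean that the plan assumes no dropout?

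*Combined protocol and SAP*

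**What the plan says.** The Protocol Summary lists the sample size as N = 120, with no word on whether these are randomised, enrolled or completing participants. Its accrual ceiling reads: "We plan to screen up to 300 subjects". Section 11.2 uses the same two numbers with other labels: "We plan on recruiting 300 subjects over the course of a year, with the anticipation that 120 will participate in the study to completion". It then adds: "This means we hope to recruit approximately 25 subjects per month".

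The order of events is clear. Eligibility is settled at the screening visit (5.1.1: "We will also collect medication and psychiatric treatment information to determine study eligibility"). Allocation follows at Visit 1 (5.1.2.1: "Participants are randomized to one of three incentive conditions"). The primary measure, change in HAM-A, runs from baseline to Visit 7 (11.4.1). No section states how many are to be randomised, the allocation ratio, the expected screen-failure rate or the expected dropout.

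**The concern.** A sample size printed beside a separate screening ceiling is usually the number enrolled or randomised. Read that way, the Summary has 120 randomised and section 11.2 has 120 finishing, which leaves no room for loss. The protocol does expect loss. Section 5.2 says "Participants may also decide to stop participating at any time", section 5.4 says "Participants are welcome to withdraw from the study at their own discretion", and section 11.1 plans to record when people stopped and to re-evaluate procedures if fewer than 25% complete as intended.

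The number 300 also shifts, from screened in the Summary to recruited in 11.2. If this were a real contradiction, the team would not know whether to stop recruiting at 120 randomised or to continue until 120 had finished, and the amount of Visit 7 data would differ accordingly.

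**Working it through.** **Inputs from the documents.** 300 screened or recruited, one year of accrual and about 25 per month (Summary and 11.2); 120 (Summary, unlabelled; 11.2, to completion); three arms (5.1.2.1). Dropout *d* is not given, so the values below are assumptions. Completion is taken as Visit 7, since section 5.4 says "The study will take place for a total of 6 weeks" and 5.5 places the follow-up appointment after participants finish. Visit 8 is also possible, because the Summary's duration of 3 months fits the 42 + 42 = 84 days from Visit 1 to Visit 8.

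**Step 1: the plan's own figure.** 300 / 12 = 25 per month, which matches 11.2. The 25 therefore belongs to the 300 and is a screening rate if the 300 are those screened. The rate for the 120 is 120 / 12 = 10 per month.

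**Step 2: overall yield.** 120 / 300 = 40%, a loss of 180. If 120 are randomised, 40% is the screening yield alone. If 120 are completers, it is screening yield times retention.

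**Step 3: the two readings.**
- Reading A, 120 randomised: completers = 120 × (1 − *d*).
- Reading B, 120 completers: randomised = 120 / (1 − *d*), rounded up. Needed screening yield = randomised / 300.

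| Assumed *d* | A: completers | B: randomised | B: screening yield |
|---|---|---|---|
| 0% | 120 | 120 | 40% |
| 10% | 108 | 134 | 45% |
| 20% | 96 | 150 | 50% |
| 40% | 72 | 200 | 67% |
| 60% | 48 | 300 | 100% |

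**Step 4: when do the Summary and 11.2 agree?** Under A, 120 × (1 − *d*) = 120 forces *d* = 0. Under B, both figures count completers, and the only limit is that no more than 300 can be randomised: *d* ≤ 1 − 120/300 = 60%. The upper end is an arithmetic limit, since it needs every screened person to be eligible. So the charge of zero dropout holds under A only, and the Summary does not say A.

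**Step 5: what depends on 120?** Section 11 states no alpha, power, effect size, standard deviation or precision target, so 120 feeds no calculation. The 25% trigger in 11.1 is a proportion of those who take part, not a count out of 120. There is no interim analysis (11.5). The comparisons in 11.4.1 and 11.4.2 use whoever was randomised and observed. None of these changes with the label.

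**The case for a change.** The best case for an edit is that reading A is the ordinary meaning of a sample size, that the text is incomplete on either reading, and that the amount of data differs. With equal allocation (assumed) and 80% retention, A leaves 96 / 3 = 32 per arm at Visit 7 and B leaves 120 / 3 = 40. For a two-arm comparison at two-sided 5% and 80% power, the normal approximation gives a detectable standardised difference of (1.96 + 0.84) × √(2/n), which is 0.70 with 32 per arm and 0.63 with 40. A feasibility pilot meant to support a grant should also keep screening yield apart from retention.

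Part of this stands. The number randomised is indeed absent, and one set of labels would read better. But the gap between 0.70 and 0.63 breaks no promise, because the plan claims no detectable difference. Recruitment under either reading would end on a head count, within the limits of 300 screened and one year, and not on the HAM-A difference between arms. Yield and retention can both be taken from the study's own records, since 11.1 already calls for completion and time of stopping.

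**Conclusion.** The concern does not call for a change. The Summary leaves 120 unlabelled and section 11.2 labels it as completers; this is a missing label in a short summary, not two conflicting targets. Zero dropout follows only if the Summary's figure is taken as the number randomised, which the documents do not say and which 5.2, 5.4 and 11.1 make unlikely as a planning assumption.

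The possible size, at assumed dropout of 10% to 40%, is 72 to 108 completers from 120 randomised, or 134 to 200 randomised for 120 completers. These figures only illustrate, as the documents give no dropout rate.

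An edit would gain little. Relabelling 120 as randomised would overwrite the one explicit label the sponsor gave, and adding a randomised target would need a retention estimate that the documents do not contain. Neither would alter the comparison, the analysis or a conclusion. Analysts can fill the gap in the usual way, by reporting the numbers screened, randomised and completing in each arm. The conclusion rests on the trial remaining a pilot with no power claim tied to 120.

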11.3 Stratification Factors

There are no planned patient stratification factors.

11.4 Analysis of Endpoints

11.4.1 Analysis of Primary Endpoints

The primary purpose of the study is to compare change in anxious symptoms from baseline to Visit 7 (end of treatment with the mobile cognitive behavior mobile application) between the three incentive conditions. The primary measure of this endpoint will be the Hamilton Rating Scale for Anxiety (HAM-A), a 14-item questionnaire measure of the severity of anxiety symptoms. The items measure both psychic anxiety and somatic anxiety, where higher scores indicate a greater presence of symptoms and lower scores indicate mild to no anxiety symptoms. Secondary measures of this endpoint will be the Anxiety Sensitivity Index (ASI) and the Leibowitz Social Anxiety Scale (LSAS). The ASI is an 18-item scale containing three subscales measuring physical, cognitive, and social concerns regarding anxiety. Higher scores reflect greater self-reported concern and lower scores reflect little self-reported concern. The LSAS is a 24-item scale measuring fear and avoidance across social situations. Higher scores indicate greater fear and avoidance severity and lower scores indicate mild to no fear or avoidance.

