5.1.2.4 Visit 4 (+7 days from Visit 3): Midpoint

Protocol # 1803019086
Version Date 12/27/2022

- Rumination Response Scale (RRS)
- Hamilton Rating Scale for Depression (HAM-D)
- Hamilton Rating Scale for Anxiety (HAM-A)

- Generalized Anxiety Disorder 7-item Scale (GAD-7)
- Patient Health Questionnaire 9 (PHQ-9)
- The Temporal Experience of Pleasure Scale (TEPS)
- Positive and Negative Affect Schedule (PANAS)
- Emotion Regulation Questionnaire (ERQ)
- Multidimensional Experiential Avoidance Questionnaire (MEAQ)
- Pittsburgh Sleep Quality Index (PSQI)
- World Health Organization Quality of Life short-form scale (WHOQOL-BREF)
- Life Events Scale for Students (LESS)
- Anxiety Sensitivity Index (ASI-3)
- Liebowitz Social Anxiety Scale (LSAS)
- Sensitivity to Punishment and Sensitivity to Reward Questionnaire (SPSRQ)
- Mobile Application Rating Scale: user version (uMARS)
- Digital Working Alliance Inventory (D-WAI)
- Medication Tracking

- Check in about how the app is working.

5.1.2. 5 Visit 5 (+7 days from Visit 4)

- Generalized Anxiety Disorder 7-item Scale (GAD-7)
- Patient Health Questionnaire 9 (PHQ-9)
- Medication Tracking
- Check in about how the app is working.

5.1.2. 6 Visit 6 (+7 days from Visit 5)

- Generalized Anxiety Disorder 7-item Scale (GAD-7)
- Patient Health Questionnaire 9 (PHQ-9)
- Medication Tracking
- Check in about how the app is working.

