10.2 Regulatory Considerations

All protocol amendments and consent form modifications will be made by the Principal Investigator.

11. Statistical Considerations

As this study is a pilot to determine feasibility of the CBT mobile application including non-monetary incentives, we do not anticipate high volume data. We intend to use the pilot data to submit an NIH grant where we will recruit a statistician to be a part of our research team.

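### The primary HAM-A comparison is stated as change from baseline with no baseline covariate; adding baseline HAM-A to the model would give equal or better precision from the same data.

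*Combined protocol and SAP*

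**What the plan says.** Section 11.4.1 is the whole of the primary analysis plan. It says "The primary purpose of the study is to compare change in anxious symptoms from baseline to Visit 7" between the three conditions, names HAM-A as the primary measure and ASI and LSAS as secondary measures, and then describes the scales. The Primary Objective in the Protocol Summary matches it: "We will compare change in anxiety from baseline to end of treatment between these three conditions". Neither place gives a test, a model or a covariate.

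Four other places bear on the point:

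- Sections 5.1.2.1, 5.1.2.4 and 5.1.2.7 list HAM-A at Visit 1, Visit 4 and Visit 7. A baseline value and a mid-treatment value are therefore already collected.
- Section 11.3: "There are no planned patient stratification factors". The design does nothing to balance baseline severity across arms.
- Section 11: "We intend to use the pilot data to submit an NIH grant where we will recruit a statistician". No one is named as responsible for choosing the model for the present trial.
- Section 11.2 expects to recruit 300 "with the anticipation that 120 will participate in the study to completion". The allocation ratio is not stated.

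**The concern.** A comparison of change scores is a baseline-adjusted comparison in which the coefficient on baseline is set to 1 instead of being estimated. Randomisation keeps it unbiased. It is inefficient, however, unless the within-arm regression slope of Visit 7 HAM-A on baseline HAM-A is 1. A slope below 1 would be unsurprising for a symptom scale rated twice, six weeks apart, in people selected for having symptoms.

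Two things are at stake. The between-arm confidence intervals may be wider than the collected data allow, in a pilot whose results are meant to support a grant application. And because the text does not settle adjusted versus unadjusted, that choice can be made after both results have been seen.

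**Working it through.** **Inputs from the documents.** Three randomised arms; N = 120; HAM-A at Visits 1, 4 and 7; no stratification. The plan gives no alpha, power, effect size, HAM-A SD, baseline-to-Visit-7 correlation or allocation ratio, so N = 120 cannot be reproduced. The only figure that can be checked is accrual: 300/12 = 25 per month, as 11.2 says.

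**Assumed.** Equal allocation, 120/3 = 40 per arm. Correlation rho = 0.3, 0.5, 0.7. SD ratio k = SD(Visit 7)/SD(baseline) = 0.8, 1, 1.25.

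**Step 1: variances.** In units of the baseline variance, per participant:

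- Change score: Var(change) = 1 + k² − 2·rho·k
- Baseline-adjusted: Var(adjusted) = k²(1 − rho²)
- Difference: Var(change) − Var(adjusted) = (1 − rho·k)²

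The difference is a square, so in large samples adjustment is never worse. The two are equal only when the slope rho·k is 1.

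Example, k = 1 and rho = 0.5: change 1 + 1 − 1 = 1.00; adjusted 1 × 0.75 = 0.75; ratio 0.75.

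| k | rho | Slope | Var(change) | Var(adjusted) | Ratio | Variance cut | SE cut |
|---|---|---|---|---|---|---|---|
| 1 | 0.3 | 0.30 | 1.400 | 0.910 | 0.650 | 35% | 19% |
| 1 | 0.5 | 0.50 | 1.000 | 0.750 | 0.750 | 25% | 13% |
| 1 | 0.7 | 0.70 | 0.600 | 0.510 | 0.850 | 15% | 8% |
| 1.25 | 0.3 | 0.375 | 1.813 | 1.422 | 0.784 | 22% | 11% |
| 1.25 | 0.5 | 0.625 | 1.313 | 1.172 | 0.893 | 11% | 5.5% |
| 1.25 | 0.7 | 0.875 | 0.813 | 0.797 | 0.981 | 2% | 1% |
| 0.8 | 0.3 | 0.24 | 1.160 | 0.582 | 0.502 | 50% | 29% |
| 0.8 | 0.5 | 0.40 | 0.840 | 0.480 | 0.571 | 43% | 24% |
| 0.8 | 0.7 | 0.56 | 0.520 | 0.326 | 0.628 | 37% | 21% |

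**Step 2: cost of estimating the slope.** With 120 participants this inflates the adjusted variance by about 1 + 1/115, under 1%. The equal-SD ratios become 0.656, 0.757 and 0.857. A simulation of 20,000 three-arm trials at each correlation gave 0.663, 0.755 and 0.856. Multiplying by 120 and rounding up, about 79, 91 or 103 participants analysed with adjustment match 120 analysed by change score.

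**Step 3: power, as an illustration.** Assume alpha 0.05 and one arm differing from the other two by 0.5 baseline SD. The noncentrality is 40 × 0.5² × (2/3)/Var = 6.667/Var. The F test has 2 and 117 df for change, 2 and 116 for adjusted; the Step 2 correction is not applied.

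| k | rho | Noncentrality, change → adjusted | Power, change → adjusted |
|---|---|---|---|
| 1 | 0.3 | 4.76 → 7.33 | 47% → 67% |
| 1 | 0.5 | 6.67 → 8.89 | 62% → 75% |
| 1 | 0.7 | 11.11 → 13.07 | 85% → 90% |
| 1.25 | 0.3 | 3.68 → 4.69 | 38% → 47% |
| 1.25 | 0.5 | 5.08 → 5.69 | 50% → 55% |
| 1.25 | 0.7 | 8.21 → 8.37 | 72% → 73% |

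**Step 4: Visit 4, a separate and smaller matter.** If every Visit 7 value is present, Visit 4 adds nothing. If a fraction m lack Visit 7 but have Visit 4, and are missing at random, using Visit 4 cuts the variance by m × r², where r is the Visit 4–Visit 7 correlation given baseline. With m = 0.20 (assumed) and r = 0.3, 0.5, 0.7: 0.20 × 0.09 = 1.8%, 0.20 × 0.25 = 5.0%, 0.20 × 0.49 = 9.8%.

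**The case against.** The strongest reply is that the plan does not choose an inefficient model, because it chooses no model. Section 11.4.1 states a purpose and a measure. Regressing change on arm and baseline HAM-A fits its wording and gives the same arm contrast as regressing the Visit 7 score. This is correct. The fault is silence, and the precision loss follows only if the text is carried out literally. But the silence is also what leaves the choice open, and the same sentence closes both gaps.

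Second, the loss may be small. Entry requires an ADIS severity rating of at least 4. If that narrows the baseline HAM-A spread, k rises above 1 and the gain shrinks. At k = 1.5 the variance cuts are 13%, 4% and 0.2% for correlations 0.3, 0.5 and 0.7. At k = 1.25 and rho = 0.8 the slope is 1 and the cut is zero. With equal SDs and rho = 0.9 it is 5%. Nothing in the documents supports k below 1, so the largest figures in the table should carry little weight. All this limits the size of the gain; it does not reverse the direction.

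Third, the study calls itself a feasibility pilot, states no power target, and leaves validity testing to later proposals. The power figures therefore show no missed target. Even so, the plan makes the three-arm comparison of anxiety change its primary purpose, so its precision matters.

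Finally, Section 11 says a statistician will join with a later grant; it does not say that none is consulted now. And the lack of stratification does not enter the variance formula; it is context only.

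**Conclusion.** The point holds. The primary comparison is stated as change from baseline, with no covariate named anywhere, although the natural covariate is collected. In large samples a baseline-adjusted comparison is never less precise, and the slope costs under 1% in variance here. This is a matter of efficiency and pre-specification, not of bias.

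The size cannot be taken from the documents. Over correlations of 0.3 to 0.7 the gain in variance is 15% to 35% with equal SDs and 2% to 22% with a Visit 7 SD 1.25 times baseline; it vanishes as the slope approaches 1. The change should be made because it is nearly free, but the trial is not invalid without it.

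**What to change.** Add to 11.4.1 a sentence such as: *Visit 7 HAM-A (or its change from baseline) will be compared between the three conditions in a linear model with baseline HAM-A as a covariate.* Do the same for ASI-3 and LSAS, each with its own baseline.

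Two smaller clarifications belong with it:

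- State how participants with a Visit 4 but no Visit 7 HAM-A will contribute, for example through a repeated-measures model or an imputation that includes Visit 4.
- In 5.1.2.1, where randomisation is listed ahead of the baseline scales, state that baseline HAM-A is completed before the arm is revealed, so that the covariate cannot be affected by knowledge of allocation.

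The cost is one or two sentences in 11.4.1, one clarification in 5.1.2.1, and one degree of freedom. No assessments or participants are added.
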